**Hepatic**

- Total bilirubin  $\leq 1.5 \times$  ULN (upper limit of normal)
- AST  $\leq 3.0 \times$  ULN, except for subjects with liver metastasis, who may only be included if AST  $\leq 5.0 \times$  ULN
- ALT  $\leq 3.0 \times$  ULN, except for subjects with liver metastasis, who may only be included if ALT  $\leq 5.0 \times$  ULN

- 10a. Subjects must have recovered from treatment-related toxicities of prior anticancer therapies to grade  $\leq 1$  (CTCAE v 5.0).

**5.2.2 Inclusion criteria for arm 1A (LAG525/spartalizumab)**

Subjects eligible for inclusion in arm 1A in this study must meet **all** of the following criteria:

1. Written informed consent must be obtained prior to any screening procedures.
2. Male or female must be  $\geq 18$  years of age at time of providing informed consent.
3. Histologically confirmed unresectable or metastatic stage IIIB/C/D or IV melanoma according to AJCC Edition 8 (refer to [Appendix 1](#))
- 4b. Previously treated for unresectable or metastatic melanoma:
  - All subjects must have received anti-PD-1 checkpoint inhibitor therapy (ie. pembrolizumab or nivolumab) either as monotherapy or in combination with ipilimumab as the last systemic therapy prior to enrollment and must have confirmed disease progression as per RECIST v1.1 (confirmed on a subsequent

scan, which can be the scan performed during screening) while on or after this therapy prior to enrollment.

- Subjects with V600*BRAF* wild-type disease must have received no more than 2 prior systemic therapies including prior anti-PD-1/PD-L1 (as monotherapy or in combination with ipilimumab)
- Subjects with V600*BRAF* mutant disease must have received no more than 3 prior systemic therapies including anti-PD-1/PD-L1 (as monotherapy or in combination with ipilimumab), and V600*BRAF* inhibitor (as monotherapy or in combination with a MEK inhibitor)
- The last dose of anti-PD-1 based therapy must have been received more than four weeks prior to first dose of study treatment.
- The last documented disease progression must have occurred within 12 weeks prior to first dose of study treatment
- No additional systemic treatment is allowed for advanced or metastatic melanoma (this includes for example tumor infiltrating lymphocyte therapy)

5a. ECOG performance status 0-1

6. At least one measurable lesion per RECIST v1.1 (refer to [Appendix 2](#))

7b. Subjects must have baseline tumor sample (fresh tumor biopsy or recent archival sample, as described in [Section 7.2.3.1.1](#)) that is positive for LAG-3 per central assessment at the Novartis-designated laboratory (Histogenex, Antwerp, Belgium)

9a. Subject must meet the following laboratory values at the screening visit in the absence of growth factors and/or transfusion support within 14 days prior to screening blood draw:

#### **Hematological**

- Hemoglobin  $\geq 9$  g/dL
- Absolute neutrophil count  $\geq 1.5 \times 10^9/L$
- Platelets  $\geq 75 \times 10^9/L$

#### **Renal**

- Serum creatinine  $< 1.5$  mg/dL

#### **Hepatic**

- Total bilirubin  $\leq 1.5 \times$  ULN (upper limit of normal)
- AST  $\leq 3.0 \times$  ULN, except for subjects with liver metastasis, who may only be included if AST  $\leq 5.0 \times$  ULN
- ALT  $\leq 3.0 \times$  ULN, except for subjects with liver metastasis, who may only be included if ALT  $\leq 5.0 \times$  ULN

10a. Subjects must have recovered from treatment-related toxicities of prior anticancer therapies to grade  $\leq 1$  (CTCAE v 5.0).

### **5.3 Exclusion criteria**

#### **5.3.1 Exclusion criteria for all arms**

Subjects eligible for this study must not meet **any** of the following criteria:

1. Subjects with uveal or mucosal melanoma
- 2a. Presence of clinically active or unstable brain metastasis at time of screening. Note: Subjects with previously unstable brain lesions who have been definitively treated with stereotactic radiation therapy, surgery or gamma knife therapy are eligible.

- Subjects with brain lesions who are untreated (including newly discovered brain lesions during screening) or received whole brain radiation must have documented stable disease as assessed by two consecutive assessments  $\geq 4$  weeks apart and have not required steroids for at least  $\geq 4$  weeks prior to randomization/enrollment.
3. Use of any live vaccines against infectious diseases within 3 months before randomization/enrollment.
  - 4a. Subjects with a condition requiring systemic treatment with either corticosteroids ( $> 10$  mg daily prednisone equivalent) or other immunosuppressive medications within 14 days of randomization/enrollment. Inhaled or topical steroids, and adrenal replacement steroid doses  $> 10$  mg daily prednisone equivalent, are permitted in the absence of active autoimmune disease.
  - 5a. Active, known or suspected autoimmune disease or a documented history of autoimmune disease. Note: Subjects with vitiligo, controlled type I diabetes mellitus on stable insulin dose, residual autoimmune-related hypothyroidism only requiring hormone replacement or psoriasis not requiring systemic treatment or conditions not expected to recur in the absence of an external trigger are permitted.
  - 6a. Active infection requiring systemic therapy (i.e. antibiotics, anti-virals, high dose steroids, immunosuppressants, or any other systemic therapy) at time of randomization/enrollment.
  7. Prior allogenic bone marrow or solid organ transplant
  8. History of known hypersensitivity to any of the investigational drugs used in this study
  9. Known history or current interstitial lung disease or non-infectious pneumonitis
  10. Malignant disease, other than that being treated in this study. Exceptions to this exclusion include the following: malignancies that were treated curatively and have not recurred within 2 years prior to start of study treatment; completely resected basal cell and squamous cell skin cancers and any completely resected carcinoma in situ
  11. Known history of testing positive for Human Immunodeficiency Virus (HIV) infection
  - 12a. Active Hepatitis B infection (HBsAg positive). Note: Subjects with antecedent of Hepatitis B (anti-HBc positive, HBsAg and HBV-DNA negative) are eligible
  13. Subject with positive test for hepatitis C virus (HCV) RNA
  14. Pregnant or nursing (lactating) women confirmed by a positive hCG laboratory test within 72 hours prior to initiating study treatment. Note: Low levels of hCG may also be considered a tumor marker, therefore if low hCG levels are detected, another blood sample at least 4 days later must be taken to assess the kinetics of the increase and transvaginal ultrasound must be performed to rule out pregnancy.
  - 15a. Women of childbearing potential, defined as all women physiologically capable of becoming pregnant, unless they are using highly effective methods of contraception during dosing and for 150-days after last dose of study treatment. Highly effective contraception methods include:
    - Total abstinence (when this is in line with the preferred and usual lifestyle of the subject). Periodic abstinence (e.g., calendar, ovulation, symptothermal, post-ovulation methods) and withdrawal are not acceptable methods of contraception
    - Female sterilization (have had surgical bilateral oophorectomy with or without hysterectomy), total hysterectomy, or bilateral tubal ligation at least six weeks before taking study treatment. In case of oophorectomy alone, only when the reproductive status of the woman has been confirmed by follow up hormone level assessment

- Male sterilization (at least 6 months prior to screening). The vasectomized male partner should be the sole partner for that subject
- Use of oral, injected or implanted hormonal methods of contraception or placement of an intrauterine device (IUD) or intrauterine system (IUS), or other forms of hormonal contraception that have comparable efficacy (failure rate <1%), for example hormone vaginal ring or transdermal hormone contraception.

NOTE: In case of use of oral contraception women should have been stable on the same pill for a minimum of 3 months before taking study treatment.

Note: Women are considered post-menopausal and not of child bearing potential if they have had 12 months of natural (spontaneous) amenorrhea with an appropriate clinical profile (i.e. age appropriate, history of vasomotor symptoms) or have had surgical bilateral oophorectomy (with or without hysterectomy), total hysterectomy, or bilateral tubal ligation at least six weeks ago. In the case of oophorectomy alone, only when the reproductive status of the woman has been confirmed by follow up hormone level assessment is she considered not of child bearing potential.

16. Sexually active males unless they use a condom during intercourse while on treatment and for 7 days after the last dose of study treatment and should not father a child in this period. A condom is required to be used by vasectomized men as well during intercourse in order to prevent delivery of the drug via semen.
- 17a. Prior systemic therapy for unresectable or metastatic melanoma with any investigational agent, or with any other agent, except anti-PD-1/PD-L1 and anti-CTLA-4 (and V600*BRAF* and MEK inhibitors if subject has V600*BRAF* mutant disease). Prior neoadjuvant and/or adjuvant therapy for melanoma completed less than 6 months before the start of study treatment.
18. Medical history or current diagnosis of myocarditis
- 19a. Cardiac Troponin T (TnT) or I (TnI) level > 2 x ULN at screening

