### Changes to the protocol

Changes to specific sections of the protocol are shown in the track changes version of the protocol using strike through red font for deletions and red underline for insertions.

Major changes are:

- Section 4.1 and protocol summary: Information has been added that enrollment in Part 1 is closed in the three initial arms (arms 1, 2 and 3) of the study.
- Section 4.2 and Section 10.7: Clarification has been added to indicate that combination arms will no longer be included in subsequent interim analyses after all subjects randomized in this arm had primary endpoint already reported in a previous interim analysis.
- Four exclusion criteria have been revised. Based on the current enrollment status in Arm 4 (i.e. 38 subjects randomized in Part 1 as of the date of release of this amendment), the changes in those exclusion criteria are not expected to affect the study population in Part 1:
  - Section 5.3.1 and protocol summary: Exclusion criterion #5 (re-numbered #5a) has been clarified to indicate that subjects with autoimmune conditions that are not expected to recur in the absence of an external trigger may be eligible.
  - Section 5.3.3: Exclusion criterion #28 (re-numbered #28a) has been corrected to remove the requirement to use central interpretation of triplicate ECGs at baseline, to align with section 7.2.2.6 stating that eligibility should be assessed by the investigator based on local interpretation of screening ECGs. It has also been clarified that the QTcF interval value (QT interval using Fridericia's correction) should be used at screening.
  - Section 5.3.3: Exclusion criterion #30 (re-numbered #30a) was revised to add uncorrected hypocalcemia as a risk factor for Torsades de Pointe and exclude subjects with such condition from receiving treatment with ribociclib, as low calcium levels can cause QT prolongation.

- Section 5.3.3: Requirements on sodium and phosphorus values at screening were removed from exclusion criterion #33 (re-numbered #33a) as abnormal sodium or phosphorus levels have no impact on QT prolongation.
- Section 6.1.1.5: Recommendations were added for investigators on dosing of ribociclib if a visit has to be delayed within the allowed visit window. It has also been clarified that shortening the rest period to less than 7 days is not recommended.

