## 6 Treatment

### 6.1 Study treatment

For this study, the terms 'investigational drugs' and 'study drugs' refer to spartalizumab, LAG525, capmatinib, canakinumab and ribociclib.

Eligible subjects will be randomized into one of the following arms and will receive the study treatment, defined as spartalizumab in combination with another investigational drug as described below and in [Table 6-1](#):

- **Arm 1:** LAG525 600 mg Q4W i.v. and spartalizumab 400 mg Q4W i.v.
- **Arm 2:** Capmatinib 400 mg BID p.o and spartalizumab 400 mg Q4W i.v.
- **Arm 3:** Canakinumab 300 mg Q4W s.c. and spartalizumab 400 mg Q4W i.v.
- **Arm 4:** Ribociclib 600 mg QD p.o on days 1 to 21 of a 28-day cycle and spartalizumab 400 mg Q4W i.v.

If a subject does not meet the specific eligibility criteria of an arm the subject will be randomized to an open arm he is eligible for with probability according to the active randomization block.

As dose-regimens for new combinations with spartalizumab become established and a RP2D has been determined, arm(s) will be added under the same master protocol upon protocol amendment. A maximum of 10 arms may be active at any given time under this master protocol.

Subjects eligible for enrollment in the non-randomized arm 1A will receive the following study treatment (also refer to [Table 6-1](#)):

- **Arm 1A:** LAG525 600 mg Q4W i.v. and spartalizumab 400 mg Q4W i.v.

All dosages prescribed and dispensed to subjects and all dose modifications (interruption, reduction/escalation, delay) during the study and the reason for the dose modification must be recorded in the eCRF (electronic Case Report Form).

Administration of i.v. investigational drugs (i.e. LAG525, spartalizumab) must take place during in-clinic visits as per the schedule defined in [Section 7](#) and [Table 6-1](#), in a facility with appropriate resuscitation equipment and a physician readily available during the period of drug administration.

Administration of s.c. investigational drugs (i.e. canakinumab) must take place during in-clinic visits as per the schedule defined in [Section 7](#) and [Table 6-1](#).

Oral investigational drugs (capmatinib, ribociclib) will be dispensed by sites to the subjects at study visits scheduled on Day 1 of each 28-day cycle, as per [Table 7-2](#).

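### Criteria 5a and 10a leave open whether a subject with a resolved life-threatening immune event on earlier anti-PD-1 therapy may enter arm 1A

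*Protocol*

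**What the plan says.** Section 5.2.2, criterion 4b, sets prior exposure for arm 1A: "All subjects must have received anti-PD-1 checkpoint inhibitor therapy", alone or with ipilimumab, as the last systemic therapy. Progression may occur on or after that therapy. The criterion does not ask why it was stopped.

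Criterion 10a in the same section reads: "Subjects must have recovered from treatment-related toxicities of prior anticancer therapies to grade" 1 or below. It sets no limit on worst past grade or type of event.

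Section 5.3.1 adds these exclusions:

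- **5a** bars active, known, suspected or documented past autoimmune disease. It then lists exceptions: vitiligo, insulin-controlled type I diabetes, replaced hypothyroidism, mild psoriasis and, last, "conditions not expected to recur in the absence of an external trigger are permitted".
- **8**: "History of known hypersensitivity to any of the investigational drugs used in this study". Section 6.1 says that the terms for these drugs "refer to spartalizumab, LAG525, capmatinib, canakinumab and ribociclib".
- **9**: "Known history or current interstitial lung disease or non-infectious pneumonitis".
- **18**: "Medical history or current diagnosis of myocarditis".

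The amendment 4 log describes the last exception in 5a as a clarification that "subjects with autoimmune conditions that are not expected to recur in the absence of an external trigger may be eligible".

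**The concern.** Arm 1A gives spartalizumab, an anti-PD-1 antibody, with LAG525 to people who have all had an anti-PD-1 antibody before. For someone whose severe immune event was provoked by that class, the external trigger is the study treatment itself. The exception in 5a makes sense when the trigger can be avoided. It does not when the arm supplies the trigger again.

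The exception has no severity limit and does not define the trigger. A site can therefore read it as admitting a subject with past Stevens-Johnson syndrome, Guillain-Barré syndrome or a grade 4 immune event. Another site can read 5a as excluding that subject.

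What is at stake is subject safety and consistent screening. Section 2.6.1 warns that immune events may be more frequent with this combination and that fatal events have occurred with the class. For myocarditis the sponsor did add a history exclusion. No effect on the response rate or its test is claimed.

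**Working it through.** No arithmetic decides this point. The check takes one test subject through the arm 1A criteria.

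**Test subject.** Had Guillain-Barré syndrome, SJS/TEN or grade 4 colitis on nivolumab plus ipilimumab. Recovered to grade 1 or below, off systemic steroids for more than 14 days, last anti-PD-1 dose more than four weeks ago, confirmed progression afterwards within the 12-week window.

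| Criterion | What it tests | Result |
|---|---|---|
| 4b | Prior anti-PD-1, progression on or after it, washout | Met |
| 10a | Current toxicity grade | Met |
| 9a | Current laboratory values | Does not test history |
| 4a | Steroids or immunosuppressants in the last 14 days | Does not exclude |
| 8 | Hypersensitivity to the five study drugs | Does not cover pembrolizumab or nivolumab |
| 9, 18 | Past pneumonitis/ILD, past myocarditis | Does not exclude; different event |
| 5a | Autoimmune disease, with exceptions | Depends on the reading |

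**The readings of 5a.** Two matters are undefined: whether a past immune-related event counts as autoimmune disease, and whether a checkpoint inhibitor counts as an external trigger.

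1. The event is not autoimmune disease: 5a does not apply and the subject enters.
2. It is autoimmune disease and the checkpoint inhibitor is the trigger: the exception applies and the subject enters.
3. It is autoimmune disease and the checkpoint inhibitor is not the trigger: the subject is excluded.

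The text does not choose among the three. Nothing else in 5.2.2 or 5.3.1 settles the case.

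**How the protocol treats the same events on study.** Section 6.3.1.3 requires permanent discontinuation for any grade 4 immune-related event. Table 6-7 requires it for SJS/TEN. Table 6-12 requires it for encephalitis, aseptic meningitis, Guillain-Barré, severe peripheral or autonomic neuropathy, transverse myelitis, and myasthenia gravis of grade 3 or higher. These rules show which events the sponsor regards as too serious for re-dosing. They do not by themselves dictate entry.

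**Subjects screened under the wording.** Arm 1A plans 20 subjects in part 1 and up to about 80 in part 2: 20 + 80 = 100. The safety DMC (Section 8.6) starts only when an arm reaches part 2, so the first 20 enter before it is active.

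**What cannot be computed.** The protocol gives neither the share of candidates with such a history nor a recurrence rate on re-exposure.

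**The case against.** The best defence is that 5a already excludes these subjects. Its general rule is broad, its other exceptions are mild or controlled states, and its mention of residual autoimmune hypothyroidism suggests that immune sequelae belong under it. An investigator would have to call the checkpoint inhibitor a trigger and then give one anyway. This stands as a possible reading, and it is why the point is an ambiguity. The text does not require it.

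The protocol also has vigilance rules for immune events, troponin monitoring, stopping rules and review of safety at interim decisions. These mitigate harm but act only after re-exposure. Candidates also have few alternatives, which argues for a narrow clause.

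A reader might infer more than the documents support:

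- **That entry rules must mirror stopping rules.** They need not. Stopping rules concern an event suspected to be caused by ongoing study drug; entry requires recovery and washout. Table 6-6 stops treatment for grade 3 liver abnormalities and Table 6-8 for grade 3 creatinine, and the fix below leaves such histories eligible.
- **That the amendment history shows an oversight.** Amendment 4 calls the change a clarification. Amendment 5 revised several common exclusion criteria and left 5a alone, which fits a deliberate choice equally well. The earlier 5a wording is not shown.
- **That reported cases measure the risk.** The grade 4 autoimmune hepatitis arose at 1000 mg LAG525, against 600 mg in arm 1A. The SJS case arose with a different partner drug. Neither is described as re-exposure after a prior event.

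**Conclusion.** The point holds as an ambiguity with a safety consequence. Taken together, 5a and 10a do not clearly exclude a subject who had a life-threatening immune event on earlier anti-PD-1-based therapy and recovered, unless the event was pneumonitis/ILD or myocarditis. Two sites applying the same text in good faith could decide differently. It is not a contradiction, and the protocol does not positively say that such subjects should enter.

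Its size is unknown. The wording governs up to about 100 subjects, all previously exposed to anti-PD-1, but the number with such a history and their recurrence risk cannot be derived. The conclusion rests only on the eligibility text and on the fact that arm 1A repeats the drug class.

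Criterion 5a applies to every arm and 10a also stands in Section 5.2.1. Section 2.2 says that no randomized arm was enrolling at amendment 5, so the practical consequence lies in arm 1A. The change should be made, but the statistical analysis does not depend on it.

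**What to change.** For arm 1A:

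1. **Clarify 5a.** State that checkpoint-inhibitor therapy does not count as an external trigger, and that immune events on prior checkpoint inhibitors are judged by item 2. Without that second part, the clarification could bar every past immune event. Criteria 9 and 18 stay as they are.
2. **Add one exclusion.** Exclude a history, on prior anti-PD-1/PD-L1-based therapy, of any clinically life-threatening or grade 4 immune-related event, SJS/TEN, encephalitis, aseptic meningitis, Guillain-Barré syndrome, transverse myelitis, severe neuropathy, or myasthenia gravis of grade 3 or higher. The only exceptions are endocrinopathy controlled with hormone replacement, type I diabetes on stable insulin, and isolated asymptomatic amylase or lipase elevation. Grade 4 ALT, AST or bilirubin is not excepted.
3. **State the choice on grade 3.** Resolved grade 3 events not named in item 2 stay eligible, except where criteria 9 and 18 apply. Present this as a benefit-risk decision, not as alignment with the on-study stopping rules.
4. **Collect the data.** Section 7.1.2.3 records relevant medical history and prior therapies but does not ask for worst grade or attribution of past immune events. Add both at screening.

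The cost is one amendment with a short clause, two screening items, and a few lost candidates in a LAG-3-selected population with limited options. How many cannot be stated from the protocol.

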### 5.3.2 Exclusion criteria specific for arm 2 (capmatinib/spartalizumab)

Subject must not meet **any** of the following criteria to be eligible for randomization in arm 2:

20. History or current diagnosis of ECG abnormalities indicating significant risk of safety for subjects participating in the study such as:
  - Concomitant clinically significant cardiac arrhythmias, e.g., sustained ventricular tachycardia, and clinically significant second or third degree AV block without a pacemaker
  - History of familial long QT syndrome or known family history of ‘Torsades de Pointes’
21. History of myocardial infarction, angina pectoris, coronary artery bypass graft (CABG) within 6 months prior to randomization.
22. Resting QTcF > 480 msec (as a mean of triplicate ECG)
23. Use of agents known to prolong the QT interval unless it can be permanently discontinued for the duration of study
24. Impairment of gastrointestinal function or gastrointestinal disease that may significantly alter the absorption of capmatinib (e.g., ulcerative diseases, uncontrolled nausea, vomiting, diarrhea, or malabsorption syndrome).

25. Subjects receiving strong inducers of CYP3A4 that cannot be discontinued or switched at least 1 week prior to randomization and for the duration of the study
26. Serum lipase > ULN
- 27a. Serum amylase grade > 2 (CTCAE v5.0). Note: Subjects with grade 1 or grade 2 serum amylase elevations at the time of randomization are eligible for Arm 2 if they are confirmed to have no signs or symptoms suggesting pancreatitis or pancreatic injury (e.g., elevated P-amylase, abnormal imaging findings of pancreas, etc)

